#### **Sensitivity Analysis 1:**

An additional sensitivity analysis will be conducted in the subgroup of FAS with Baseline fasting TG < 500 mg/dL, in which all patients who have missing data due to discontinuation will be considered as non-responders.

#### **Sensitivity Analysis 2:**

A 2-dimensional tipping-point analysis will be conducted in the subgroup of FAS with Baseline fasting TG < 500 mg/dL using the imputed data based on the primary imputation approach as described in Section 4.9.1.4 in the SAP. Similar to the sensitivity analysis 5 for the primary endpoint, a positive constant shift values (%) will be added to or subtracted from the percent change of the imputed TG values at each time point of interest until the tipping points are reached.

#### 4.9.3.3 *Percent Change in Fasting ApoC-III, VLDL-C, Remnant Cholesterol, Non-HDL-C, HDL-C, TC, ApoB, LDL-C, and ApoA-1 From Baseline at Month 6 and at Month 12*

The percent change in fasting apoC-III, VLDL-C, remnant cholesterol, non-HDL-C, HDL-C, TC, apoB, LDL-C, and apoA-1 from Baseline to Months 6 and Month 12 in the FAS will be analyzed in the way similar to that for the primary endpoint using an ANCOVA model with percent change from Baseline to Month 6 or Month 12 in fasting value as the dependent variable, treatment group (olezarsen 80 mg, olezarsen 50 mg, or Placebo) and baseline stratification factor as factors, and natural log-transformed baseline value as a covariate.

The sensitivity analyses using the imputation models as described in sensitivity analysis 3 and 5 for the primary endpoint will be conducted.

4.9.3.4 *Proportion of Patients Who Achieve Fasting TG < 500 mg/dL at Month 6 and at Month 12 in the Subgroup of Patients with Baseline fasting TG  $\geq$  500 mg/dL*

The proportion of patients who achieve fasting TG < 500 mg/dL at Month 6 and Month 12 will be analyzed in the same way as the proportion of patients who achieve fasting TG < 150 mg/dL. It will be conducted in the subset of FAS with baseline fasting TG  $\geq$  500 mg/dL. Tipping point analysis will not be performed.

4.9.3.5 *Adjudicated Acute Pancreatitis Event Rate During the Treatment Period in the FAS*

All AEs and SAEs that occur during the study that are consistent with an event of acute pancreatitis will be adjudicated by a blinded, independent committee according to the Atlanta classification of acute pancreatitis and as outlined in the PAC. These events will be categorized by the various criteria to be one of the following: 1) documented pancreatitis, 2) probable pancreatitis, 3) possible pancreatitis, 4) unable to adjudicate, and 5) no diagnosis of acute pancreatitis. For the purposes of data analysis, events that are documented, probable or possible are to be considered adjudicated acute pancreatitis. A listing will be provided to display each adjudicator's and the final adjudication committee's classification results for each event. The adjudicated acute pancreatitis event rates will be compared between pooled olezarsen treatment and placebo group using a Negative Binomial regression model or Poisson regression model with the treatment group and natural log transformed baseline fasting TG as the factors, and number of adjudicated acute pancreatitis events in 5 years prior to the enrollment as a covariate. The logarithm of time in year that each patient observed during the Treatment Period will be used as an offset variable.

From the models, the mean rate and SEM for each treatment group as well as the mean rate ratio relative to the placebo group and corresponding 95% CIs will be estimated. The p-value of Wald-based chi-square test will also be reported.

Week 53 is defined as Day 379 (scheduled visit day plus a 14-day window) or the last contact date within the study, whichever is earlier. If patients have intercurrent event(s) before Week 53, the Treatment Policy strategy will be implemented, the pancreatitis events occurred post intercurrent events will continue to be collected. All adjudicated pancreatitis events including those post the intercurrent events will be included in the analysis. For patients who discontinued the treatment early and were lost to follow-up before Week 53, the pancreatitis event rate will be adjusted by the length of observation time in the analysis model.

The sample SAS code for the Negative Binomial regression model can be found below:

```

/*****
/* Note*/
/* logbase      = log transformed baseline TG                               */
/* trtpn = treatment group: 0=pooled placebo, 1=olezarsen 80 mg or 50 mg      */
/* numevent = number of adjudicated acute pancreatitis events                */
/* num5year = number of adjudicated acute pancreatitis events in 5 years prior to  */
/*           the enrollment                                                    */
*****/

data pan; set pan;
    logtime = log(years);
run;

proc genmod data=pan;
    class trtpn;
    model numevent = trtpn logbase num5year/dist=negbin link=log
        offset = logtime;
    /* update "dist=negbin" to "dist=poisson" for Poisson regression model*/
    lsmeans trtpn/diff cl exp ilink;
run;

```

In the case of not enough acute pancreatitis events to perform the model-based analysis, the number and percentage of subjects with the acute pancreatitis event along with the two-sided 95% exact CI using Clopper- Pearson methodology will be summarized based on FAS. Fisher's exact p-value will also be provided.

#### 4.9.3.6 Adjudicated Acute Pancreatitis Event Rate during the Treatment Period in the Subset of FAS with $\geq 2$ Events of Adjudicated Acute Pancreatitis in 5 Years Prior to Enrollment

The data will be analyzed in the same way as described in Section 4.9.3.5.

## 4.10 Safety Evaluation

All safety summaries will be based upon the Safety Set. By-visit safety data will be presented using visit label as recorded on the eCRF per Schedule of Procedures in Appendix A of the protocol.

### 4.10.1 Extent of Exposure and Treatment Compliance

The duration of exposure to olezarsen will be calculated as follows:

- Treatment exposure (days) = date of last Study Drug administration – date of first administration + 28
- Treatment exposure (months) = Treatment exposure (days)/30
- Treatment Compliance (%) = (actual total dose injected [mg]) / (expected total dose to be administered during the treatment period [mg])  $\times$  100.

Note that for patients who early terminated from treatment, denominator should be based on the total doses expected (mg) until discontinuation.

The following summaries will be provided by treatment group and olezarsen treated and listed based on Safety Set:

- A summary of the treatment exposure in both days and months, total number of doses administered, and the total amount of study drug received (mg)
- A summary of treatment compliance (%).

- Number of patients with dose interruption, dose interruption due to AE, and number of patients with study drug reduced.
- Descriptive summary of number of days of dose interruption

The following listings will be provided:

- A by-subject listing of administration of study drug
- A by-subject listing of treatment compliance (%)

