### **1.2.4. Safety and Tolerability Endpoints**

Safety and tolerability assessments include: adverse events, vital signs and weight, physical examinations, clinical laboratory tests, electrocardiogram (ECG), and use of concomitant medications. Safety and tolerability results in patients receiving olezarsen will be compared with those receiving placebo.

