### 3 EXPERIMENTAL PLAN

#### 3.1 Study Design

This is a multi-center, randomized, double-blind, placebo-controlled study done in conjunction with the TIMI Study Group, an academic research organization based at Brigham and Women's Hospital and Harvard Medical School. Eligible patients will enter an approximately 4-week Screening Period (that may be extended to 8 weeks if assessments can't be completed within the 4-week period) that includes an at least 2-week Diet/life-style Stabilization/Run-in Period, and an approximately 2-week Qualification Period. Following Qualification, approximately 152 eligible patients will be randomized 1:1 to Cohort A (50 mg) or Cohort B (80 mg) and each cohort further randomized 3:1 to receive olezarsen or placebo in a 53-week Treatment Period. Patients in Cohort A will receive 50 mg of olezarsen once every 4 weeks or matching volume of placebo (0.5 mL) during Weeks 1-49 of the Treatment Period. Patients in Cohort B will receive 80 mg olezarsen once every 4 weeks or matching volume of placebo (0.8 mL) during Weeks 1-49 of the Treatment Period. The 80 mg dose (blinded olezarsen or placebo) may be adjusted to 50 mg every 4 weeks due to tolerability or safety reasons at any point during the study following consultation with the Sponsor Medical Monitor or designee. Randomization will be stratified by Qualification fasting TG levels of < 500 mg/dL vs. ≥ 500 mg/dL. Following the Week 53 visit, patients will enter the 13-week Post-Treatment Follow-up Period. All endpoints will be evaluated after the last patient has completed the Week 53/ET Visit.

**The patients, Investigators, study staff, and the Sponsor are to remain blinded to lipid data (central and local) starting after the first dose on Day 1 then throughout the remainder of the study or as noted for TG or apoB alerts per Section 8.5.7 of the protocol.**

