#### 3.3 Number of Patients

Approximately 152 patients are planned to be enrolled in this study.

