  - b. Obtain further history for concomitant drug use (including non-prescription medications, herbal and dietary supplement preparations), alcohol use, recreational drug use, and special diets
  - c. Obtain a history for exposure to environmental chemical agents and travel
  - d. Serology for viral hepatitis (HAV IgM, HBsAg, HCV antibody, cytomegalovirus (CMV) IgM, and EBV antibody panel)
  - e. Serology for autoimmune hepatitis (e.g., antinuclear antibody [ANA], and/ or anti-smooth muscle antibody [SMA])

\*Additional liver evaluations, including gastroenterology/hepatology consultations, hepatic CT or MRI scans, may be performed at the discretion of the Investigator, in consultation with the Sponsor Medical Monitor or designee.

4. Patients having alternative explanation for liver chemistry elevations may restart Study Drug at the original dose when ALT and AST levels become  $\leq 3 \times \text{ULN}$  (or below  $2 \times \text{baseline}$  if the baseline value was  $> \text{ULN}$ ) and following consultation with the Sponsor Medical Monitor or designee who must assess that alternative etiology is well supported as the likely cause.
5. Patients without alternative explanation for liver chemistry elevations but not yet meeting permanent Stopping Rules as described in bullet #6, must have Study Drug dose permanently reduced to 50 mg, if on an 80-mg dose (blinded olezarsen or placebo). Patients treated with 50-mg dose should remain on this dose.

6. Patients without alternative explanation for liver chemistry elevations and **meeting any of the following criteria must have Study Drug stopped permanently\*\***; values that are not confirmed due to failure to retest or missing lab values will be presumed confirmed:
- ALT or AST  $> 8 \times$  ULN, which is confirmed
  - ALT or AST  $> 5 \times$  ULN, which is confirmed and persists for  $\geq 2$  weeks
  - ALT or AST  $> 3 \times$  ULN (or the greater of  $2 \times$  baseline value or  $3 \times$  ULN if the baseline value was  $> \text{ULN}$ ), which is confirmed **and** total bilirubin  $> 2 \times$  ULN or INR  $> 1.5$
  - ALT or AST  $> 3 \times$  ULN (or the greater of  $2 \times$  baseline value or  $3 \times$  ULN if the baseline value was  $> \text{ULN}$ ), which is confirmed, **and** the new appearance (i.e., onset coincides with the changes in hepatic enzymes) of fatigue, nausea, vomiting, right upper quadrant pain or tenderness, fever, rash, and/or concomitant eosinophilia ( $> \text{ULN}$ )

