**For end dates:**

Imputation will be performed for the end date only if the day or month is missing (i.e., year is present) for a resolved AE as follows:

- If month and day are missing and year is:
  - the same as the year of the last dose of Study Drug, then assign the month-day of the last dose of Study Drug
  - otherwise, assign December 31
- If only day is missing, then assign the last day of the month.

If the imputed start date is later than the imputed end date, then set the imputed start date to the imputed end date.

*4.10.2.4 Adverse Events of Special Interest*

The following AEs are considered AE of special interest for the study. These events will be reviewed and evaluated to determine if they meet the criteria.

- Platelet count < 50,000/mm^3 accompanied by a major bleeding (MB) event or clinically relevant non-major bleeding (CRNMB) event, or platelet count of < 25,000/mm^3 irrespective of a MB or CRNMB event.
- Use of medications (prophylactic treatment such as antihistamines, acetaminophen, non-steroidal anti-inflammatory drugs [NSAIDs], corticosteroids, etc.) as pre-treatment to avoid a hypersensitivity reaction or recurrence of a previous hypersensitivity reaction.

Those events will be individually reviewed and evaluated to determine if they meet the criteria.

The following analyses will be provided.

- The number and percentage of patients experiencing events as well as the total number of reported events, risk difference and its 95% CI in the crude incidence rates between each active treatment group (or total olezarsen treated) and pooled placebo group, classified by PT, will be tabulated by treatment group and total olezarsen treated.
- A cumulative incidence plot if data supported.
- EAIR, risk difference and its 95% CI in EAIRs between each active treatment group (or total olezarsen treated) and pooled placebo group, and EAER. classified by PT, will be tabulated by treatment group and total olezarsen treated.

*4.10.2.5 Other Adverse Events of Interest*

The number and percentage of patients experiencing events as well as the number of reported events, risk difference and its 95% CI in the crude incidence rates between each active treatment group (or total olezarsen treated) and pooled placebo group, classified by PT (unless otherwise specified), will be tabulated by treatment group for the following AEs of Interest.

*4.10.2.5.1 Bleeding TEAEs*

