#### 4.10.2.5.3 Hypersensitivity TEAE

Hypersensitivity TEAEs will be analyzed for the following categories.

- Hypersensitivity TEAE (defined based on the Hypersensitivity SMQ [narrow scope only]) by SOC and PT
- TEAEs in the Hypersensitivity FMQ (narrow) by PT.
- Serious TEAEs, fatal TEAEs and TEAEs leading to treatment discontinuation in the Hypersensitivity FMQ (narrow) by PT
- Action taken with drug due to TEAEs in the Hypersensitivity FMQ (narrow)
- Rescue medication used in management TEAEs in the Hypersensitivity FMQ (narrow)
- TEAEs in the Hypersensitivity FMQ (broad search, incorporates broad and narrow FMQ preferred terms to maximize sensitivity) by PT.
- Serious TEAEs, fatal TEAEs and TEAEs leading to treatment discontinuation in Hypersensitivity FMQ (broad search, incorporates broad and narrow FMQ preferred terms to maximize sensitivity) by PT
- Action taken with drug due to TEAEs in the Hypersensitivity FMQ (broad search, incorporates broad and narrow FMQ preferred terms to maximize sensitivity)
- Rescue medication used in management TEAEs in Hypersensitivity FMQ (broad search, incorporates broad and narrow FMQ preferred terms to maximize sensitivity)
- TEAEs in the Hypersensitivity algorithmic FMQ. The FMQ definition is using an algorithmic component of the PTs identified within the Hypersensitivity FMQ based on the locations that hypersensitivity is known to commonly affect, i.e., airway, skin, soft tissue, and systemic. In addition, the onset of event(s) is within 7 days of the treatment.
- TEAEs in the Anaphylactic reaction FMQ (narrow) by PT
- Serious TEAEs, fatal TEAEs and TEAEs leading to treatment discontinuation in Anaphylactic reaction FMQ (narrow) by PT

For patients who had hypersensitivity reactions, either in FMQ narrow, broad, or algorithmic, the time to onset of the first event will be summarized using descriptive statistics.

For patients who had serious hypersensitivity reactions or discontinued study drug due to hypersensitivity reactions, either in FMQ narrow, broad, or algorithmic, a graphical patient profile including selected laboratory tests will be provided.

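### SAP 4.10.1 counts dose reductions over a pooled placebo column, about half of which comes from a cohort with no defined lower dose, so the by-dose reading of that one row is distorted

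*Combined protocol and SAP*

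**What the plan says.** **Who can be reduced.** Protocol Section 3.1 states: "The 80 mg dose (blinded olezarsen or placebo) may be adjusted to 50 mg every 4 weeks due to tolerability or safety reasons". Two safety rules name a reduction, and both use the same step for blinded olezarsen or placebo: Section 8.5.1 step 5 (liver) and footnote 3 to Table 2 (platelets). The liver step adds: "Patients treated with 50-mg dose should remain on this dose". No level below 50 mg is defined anywhere. Section 8.6, however, allows the dose to be lowered for safety or tolerability without naming a cohort.

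**Allocation.** Patients are "randomized 1:1 to Cohort A (50 mg) or Cohort B (80 mg) and each cohort further randomized 3:1 to receive olezarsen or placebo" (protocol Section 3.1). Section 3.3 gives the planned size: "Approximately 152 patients are planned to be enrolled in this study".

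**Reporting.** SAP 4.10.1 plans, for each treatment group and for olezarsen overall, "Number of patients with dose interruption, dose interruption due to AE, and number of patients with study drug reduced". SAP 4.2.1 names the groups as placebo, 50 mg and 80 mg, presents safety data by group plus total olezarsen, and reports categorical data as counts and percentages by default. Nothing in 4.10.1 splits placebo by cohort or limits the denominator to patients who can be reduced. Protocol Section 1.2.4 sets the general intent: "Safety and tolerability results in patients receiving olezarsen will be compared with those receiving placebo".

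**The concern.** Pooling placebo across cohorts works when every placebo patient can have the event being counted. On this row, half of them have no defined route to it. The 80 mg column, where every patient can be stepped down, sits beside a placebo column where only about half can. The 50 mg column, where no step is defined, sits beside the same half-eligible column.

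So with no drug effect on dose reduction, the row would still show 80 mg reduced more often than placebo and 50 mg less often. The cause is eligibility, and more patients would not remove it. The trial compares two doses, and reduction for tolerability is an item a reader will consult when choosing between them.

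**Working it through.** The plan gives no reduction rate and no planned size for the placebo group at 152 patients, so there is no stated figure for this row to reproduce. The sizing statement (protocol Section 10.2) uses 33, 33 and 22, a 3:3:2 split, which serves as a check on the allocation. The power calculation does not enter.

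**1. Group sizes** (planned total 152; 1:1, then 3:1)
- Per cohort: 152/2 = 76.
- Olezarsen per cohort: 76 × 3/4 = 57. Placebo per cohort: 76 × 1/4 = 19.
- Pooled placebo: 19 + 19 = 38. The split 57:57:38 is 3:3:2, matching the sizing statement.
- Cohort A share of pooled placebo: 19/38 = 50%.

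**2. Pooled placebo rate**
Let rA and rB be the reduction rates in Cohort A and Cohort B placebo. The pooled rate is (19·rA + 19·rB)/38 = (rA + rB)/2. Under the specific reduction rules rA = 0. Writing r for rB, the pooled rate is r/2.

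**3. Effect on the by-dose contrasts**
Let s be the rate on olezarsen 80 mg.
- Against Cohort B placebo: s − r.
- Against pooled placebo: s − r/2, which is larger by r/2.
- 50 mg against pooled placebo: 0 − r/2 = −r/2.

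With no drug effect (s = r), for assumed values of r:

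| r (assumed) | Expected reductions, 80 mg (57r) | Expected reductions, Cohort B placebo (19r) | Pooled placebo shows | 80 mg minus pooled placebo | 50 mg minus pooled placebo |
|---|---|---|---|---|---|
| 0% | 0 | 0 | 0% | 0 | 0 |
| 2% | 1.14 | 0.38 | 1.0% | +1.0 | −1.0 |
| 5% | 2.85 | 0.95 | 2.5% | +2.5 | −2.5 |
| 10% | 5.7 | 1.9 | 5.0% | +5.0 | −5.0 |
| 20% | 11.4 | 3.8 | 10.0% | +10.0 | −10.0 |

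Differences are in percentage points; the true 80 mg minus placebo difference is zero in every line.

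**4. In whole patients**
One reduced Cohort B placebo patient is 1/38 = 2.6% as planned and 1/19 = 5.3% among those who can be reduced. Two are 2/38 = 5.3% and 2/19 = 10.5%.

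**5. Total olezarsen against pooled placebo**
Total olezarsen shows 57s/114 = s/2, and pooled placebo shows r/2. The ratio is s/r, as in Cohort B. The absolute difference is (s − r)/2, half the Cohort B difference, and is zero when s = r.

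**The case against.** **This is a descriptive row.** SAP 4.10.1 attaches no risk difference, interval or p-value to it. That stands: no planned estimate or test in that section is biased, and the risk is that one row is misread.

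**A broader reading is tempting but not supported.** A reader might infer that the whole 80 mg tolerability comparison is biased. Adverse events, discontinuations, dose interruptions, laboratory abnormalities and injection-site reactions can occur in both cohorts, so the eligibility problem does not arise for them.

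**A formal contrast might be inferred from SAP 4.10.2.5.** Its lead-in plans "risk difference and its 95% CI in the crude incidence rates between each active treatment group (or total olezarsen treated) and pooled placebo group", and the outputs beneath it include action taken for hypersensitivity events, where Reduced Dose is one of five categories (protocol Section 9.4.3.3). The SAP does not spell out a risk difference for each action category. For an established hypersensitivity reaction, protocol Section 8.5.6 speaks of discontinuation, not reduction. These tables add little.

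**The rate may be very low.** In the Phase 2 study no patient met a liver monitoring rule or had a confirmed platelet count below 100,000/mm³ (protocol Section 2.3.4); findings of those kinds trigger the two rules that name a reduction. Section 8.6 also discourages adjustment before Week 25. This is fair: the documents give no support for 10% to 20% on placebo, and at 5% only about one placebo reduction is expected. Reductions for other tolerability reasons remain possible, and r is unknown in advance.

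**Section 8.6 names no cohort.** It is therefore too strong to say that a Cohort A patient cannot be reduced; what holds is that no lower level is defined for them. If Cohort A placebo patients were reduced, the overstatement would be (rB − rA)/2 instead of r/2. The liver rule's instruction for 50 mg patients belongs to that rule and is not a general statement about Cohort A.

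**The data are recoverable.** A by-subject listing of administration is planned, and table shells, which might carry footnotes, are not in the documents. A listing lets a careful reader rebuild the comparison; it does not correct the table.

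**Conclusion.** The point holds as a minor reporting flaw in one descriptive row. Following the SAP text, any placebo percentage for study drug reduced is about half the Cohort B placebo rate, so the by-dose reading is off by r/2: upward for 80 mg against placebo, downward for 50 mg. The size is zero if no Cohort B placebo patient is reduced, and 1 to 5 points for assumed r of 2% to 10%.

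This rests on three assumptions: the planned allocation is roughly achieved among dosed patients, the only reduction used is the defined step from the 80 mg level, and the row is shown with percentages, as SAP 4.2.1 provides by default. The ratio of total olezarsen to pooled placebo is unaffected, although its absolute difference is diluted by half.

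**What to change.** - In SAP 4.10.1, and for the Reduced Dose category wherever action taken is tabulated, report reductions for olezarsen 80 mg against Cohort B (0.8 mL) placebo on Cohort B denominators. Showing placebo by cohort on this row would also do.
- Mark the row not applicable for olezarsen 50 mg and Cohort A placebo, subject to the reconciliation below.
- Keep the total olezarsen against pooled placebo line, and leave every other safety comparison against pooled placebo as planned.
- Reconcile the open wording on lowering the dose in protocol Section 8.6 with the specific reduction rules in Sections 3.1 and 8.5, so that it is clear which patients can appear in this row. The choice of rule is for the sponsor.

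The cost is one SAP sentence and a denominator change in a few tables; cohort is already in the randomisation data. The downside is a placebo denominator of about 19 instead of 38, with less precision for this single item.
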